The psychologists from the study will be either licensed psychologists or master students at clinical psychology and psychotherapy. They will support the participants' adherence by providing reminders using the messaging application available in the platform or via telephone, offering feedback, and monitoring the progress as well as risk for deterioration. Any crisis or any other adverse events are reported to the research team. In cases when participants forget to complete one session, the psychologists will offer reminders and send messages to participants by using platform messages and telephone messages.

Assessments

Instruments

The selected instruments have already been well established and frequently used in CBT trials for posttraumatic stress disorder in particular, as well as for other anxiety and mood disorders.

Table 2 Measurements and time assessment

Instruments	Abbreviation	Aim	Time of assessment
Clinical administered			
Posttraumatic Stress Disorder Symptom Scale Interview for DSM-5	PSS-I-5	PTSD symptoms	Pre and post treatment assessment (11) weeks
Alcohol Use Disorder Identification Test	AUDIT	Abuse and dependence of alcohol	Screening and exclusion participants with excessive drinking problems
Semi-structured clinical interview for DSM-IV	PDSQ	DSM-IV axis I severity	Pre and post treatment assessment (11) weeks
Self-report ratings			
Primary outcome			
Posttraumatic Diagnostic Scale for DSM-5	PDS-5	Severity of PTSD symptoms	Pre-treatment, middle intervention assessment (after 6 weeks), post-treatment and

			follow-up assessment (3 months)
The Posttraumatic Cognitions Inventory	PTCI	Catastrophic cognitions	Pre-treatment, middle intervention assessment (after 6 weeks), post-treatment and follow-up (3 months)
PTSD Checklist	PCL-5	Screening, monitor	Pre-treatment, every week, middle intervention assessment (after 6 weeks), post-treatment and follow-up (3 months)
Secondary outcome			
Patient health questionnaire-9	PHQ-9	Symptoms and severity of depression	Pre-treatment, every week, middle intervention assessment (after 6 weeks), post-treatment and follow-up (3 months)
General Anxiety Disorder	GAD-7	Symptoms of general anxiety disorder	Pre-treatment, every week, middle intervention assessment (after 6 weeks), post-treatment and follow-up (3 months)
The work and social adjustment scale	WSAS	Functional impairment	Pre-treatment, middle intervention assessment (after 6 weeks), post-treatment and follow-up (3 months)

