The primary outcome measures PTSD Symptom Scale - Interview for DSM-5 (PSS-I-5); Posttraumatic Diagnostic Scale for DSM-5 (PDS-5) (Foa et al., 2016); and PTSD Checklist for DSM-5 (PCL-5) (Bovin et al., 2016).

Posttraumatic Stress Disorder is assessed using the Romanian adapted version of PTSD Symptom Scale - Interview for DSM-5 (PSS-I-5). PSS-I-5 is originally a face-to-face semi-structured interview that assesses PTSD symptoms in the past months developed by Foa et al. The semi-structured interview contains 24 items that assess PTSD according to DSM-5 criteria. This traumatic event is called "trauma index" and the remaining criteria for the diagnosis are evaluated according to this event. There are 20 items which address symptoms criteria according to DSM-5 clusters: intrusions (items 1-5), avoidance (items 6-7), change in mood and cognition (items 8-14) and arousal and hyperactivity (items 15-20). These items evaluate the frequency of symptoms in the last month for the trauma index. Participants answer on a 5 point Likert scale ranging from 0 (not at all) to 4 (6 or more times a week/severe).

Symptoms are considered present when rated as 1 or higher. PSS-I-5 symptom severity is calculated by summing the items 1-20 (scores range between 0 and 80). Items 21 and 22 assess for overall distress and interference and items 23 and 24 report delayed onset and duration of symptoms, respectively. PTSD diagnosis is consistent with DSM-5 criteria and it requires presence of 1 intrusion symptom, 1 avoidance symptom, 2 cognition and mood

symptoms and 2 arousal symptoms for a period of 1 month. A significant distress or interference is also necessarily to be present (operationalized as a score of 2 or higher on either item 21 or 22).

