Posttraumatic Diagnostic Scale for DSM-5 (PDS-5). The PDS-5 (Foa et al., 2016) is a 24-item self-report questionnaire that supplements the administration of PSS-I-5. The questionnaire includes a trauma screen, followed by 20 questions corresponding to PTSD symptom according to DSM-5 criteria and offers an estimation of PTSD severity of symptoms. Participants are asked to complete the questionnaire in correspondence with “trauma index”. There are 4 clusters which assess distress, interference, onset and duration of symptom. The participants answers on a 5 point Likert scale ranging from 0 (not at all) to 4 (6 or more times a week/severe). In cases where there are multiple traumatic events, “trauma index” is evaluated as the most traumatic event, the event which currently produces the most distressing experience.

PTSD Checklist for DSM-5 (PCL-5). This scale has different versions; in our study we will use the version for the civilian population. PCL is 20 item self-report questionnaires that prompt informants to endorse the level of distress that has co-occurred according to each PTSD symptom in the previous month. PCL is used for screening, temporary diagnostic and for monitoring the symptoms on 5 point Likert scale (0 to 4) (Ruggiero, Del Ben, Scotti & Rabalais, 2003). PCL-5 total score ranges from 0 to 80, with higher score indicating greater PTSD symptom severity. PCL has excellent internal consistency (Cronbach $\alpha=.96$) and a high level of stability over time, test-retest reliability .84. Scores of 31 or 33 was demonstrated to be optimally efficient to diagnose PTSD (Bovin et al., 2016). In the study we will use PCL-5 for screening and to monitor progress and symptoms of PTSD. Participants will complete PCL-5 weekly.

Secondary outcomes

Secondary outcome measures include depressive symptoms, functional impairment, quality of life, cognitions related to trauma, stress level and other anxiety symptoms.

General mood

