The effect size for iCBT intervention for PTSD is considered to be small to medium (Kuester, Niemeyer & Knaevelsrud, 2016; Lewis et al., 2019; Sibrandij, Kunovski & Cuijpers). Take this information in consideration we expected an effect size of .60. Based on this effect size, a power of .80 and a level alpha of 0.05 we would need 45 participants in each condition for testing the two tails hypothesis. This recommended sample size has been increased to accommodate an attrition rate of 20%. Thus, the study aims to achieve a total sample of 108.

Statistical analysis

All statistical analyses will be performed using the IBM SPSS Statistics version 20. The aim analysis will be conducted on intention-to-treat samples. We will use a linear mixed effects models approach with full information maximum likelihood estimation. This approach was recommended since it uses all available data and can handle missing data appropriately (Gueorguieva & Krystal, 2004; Meyer et al., 2015; Pond, 2011). The approach emphasizes the assumption that data are randomly missing and does not assume that missing data remain stable as in the last-observation-carried-forward (LOCF) approach (Blankers, Koeter & Schippers, 2010; Meyer et al., 2015). Significance testing of dichotomous data such as diagnostic status will be conducted with chi-square tests. Calculation of within and between- groups effect sizes (Cohen d) will be based on the pooled standard deviations. Regression analyses will be used to identify predictors of treatment outcome. Moderation and mediation analysis will be conducted with multiple regression models, using the PROCESS macro for SPSS (Hayes, 2017), a computational technique that can compute both simple and complex moderation and mediation models. Effect sizes for significant effects will be indicated by Cohen's d.

Consistent with recommendations from CONSORT (Schulz, Altman, Moher, 2011) and SPIRIT (Chan et al., 2013) we mention our intention to perform secondary analyses for minimal treatment users, defined as participants that complete at least 5 of recommended modules and use the intervention program for at least 80 minutes. This definition is based on the specific of our intervention program and the criteria used in other studies (Ciuca et al., 2011; Meyer et al., 2015; Ivarsson et al., 2014).

Discussion

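### The protocol gives conflicting lists of primary outcomes and no success rule for several primaries, while the sample size assumes a single unnamed outcome

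*Protocol*

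**What the plan says.** Four places in the protocol bear on this.

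- **Primary outcomes section.** Three scales are named: "The primary outcome measures PTSD Symptom Scale - Interview for DSM-5 (PSS-I-5); Posttraumatic Diagnostic Scale for DSM-5 (PDS-5") "and PTSD Checklist for DSM-5 (PCL-5").
- **Table 2.** Three self-reports stand under the primary-outcome label: PDS-5, "The Posttraumatic Cognitions Inventory" (PTCI) and PCL-5. The row "Posttraumatic Stress Disorder Symptom Scale Interview for DSM-5" stands higher up, in the clinician-administered block, without a primary or secondary label.
- **Secondary outcomes section.** "Secondary outcome measures include depressive symptoms, functional impairment, quality of life, cognitions related to trauma, stress level and other anxiety symptoms". The PTCI is the only scale described under the later subheading on cognitions, so this sentence makes it secondary.
- **Sample size section.** With an effect size of .60, "a power of .80 and a level alpha of 0.05 we would need 45 participants in each condition", two-tailed. No outcome is named. This is the only alpha in the document.

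The Statistical analysis section describes a mixed model for the continuous outcomes. It gives no order of outcomes, no rule for declaring success on several primaries and no primary time point.

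**The concern.** The primary outcome decides whether the trial can claim success. Here the PTCI is both primary and secondary, and the interview is primary in the text but unlabelled in the table. Two people reading the protocol in good faith could analyse different primary sets.

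The choice carries weight in this design. Participants cannot be blinded and the control is a waiting list, whereas the Blinding section says that the clinical interviewers are blind to allocation. Among the four scales involved, PSS-I-5 is therefore the only one rated by a blinded assessor. The three scales under Table 2's primary label are all self-reports by participants who know their group.

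The sample size adds a second problem. It was worked out for one test, and the protocol does not say which scale that test belongs to or how three would be combined.

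**Working it through.** **Inputs.** From the Sample size section: d = 0.60, two-sided alpha 0.05, power 0.80, 45 per condition. Three primary scales come from the Primary outcomes section. The correlation between the scales' test statistics is not given. I assume a common value ρ between 0 and 0.9. High values are plausible because the three PTSD scales rate the same DSM-5 symptoms.

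**Step 1: the plan's own figure.** An exact two-sample t-test at d = 0.60 needs 44.6, so 45 per arm, and has 80.4% power at 45. The normal approximation gives δ = 0.60 × √(45/2) = 2.846 and power Φ(2.846 − 1.960) = 81.2%. The stated 45 reproduces, for one outcome.

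**Step 2: success on any one of three, each at 0.05.** If independent, the error is 1 − 0.95³ = 14.3%. With correlation ρ and c = 1.96 it is

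1 − ∫ φ(x) [Φ((c − √ρ·x)/√(1−ρ)) − Φ((−c − √ρ·x)/√(1−ρ))]³ dx.

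Half of a two-sided error points to harm, so I also give the part in favour of treatment (one-sided 0.025 per scale; 2.5% for a single test).

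**Step 3: success only if all three are significant.** There is no alpha inflation, but at d = 0.60 on every scale the power is

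∫ φ(x) [Φ((δ − c + √ρ·x)/√(1−ρ))]³ dx.

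At ρ = 0 this is 0.812³ = 53.6%.

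| ρ | Any of three: two-sided error | Any of three: in favour of treatment | All three: power |
|---|---|---|---|
| 0 | 14.3% | 7.3% | 54% |
| 0.5 | 12.5% | 6.3% | 63% |
| 0.7 | 10.9% | 5.5% | 68% |
| 0.8 | 9.8% | 4.9% | 70% |
| 0.9 | 8.4% | 4.2% | 74% |

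The power column uses the normal approximation. Starting from the t-test power instead lowers it by one to two points (0.804³ = 52% at ρ = 0).

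**Step 4: three primaries with an alpha split.** At 0.05/3 = 0.0167, power for one given scale with 45 per arm is 65.7%, and 80% needs 60 per arm (59.6 before rounding). Power to win on at least one of three at that level is about 84% at ρ = 0.7, 81% at 0.8 and 77% at 0.9. The cost of a split therefore depends on which claim is to be powered.

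**The case against.** **No testing rule is stated.** A reader might infer that every listed scale will be tested at an uncorrected 0.05. The protocol does not say so: its only alpha belongs to the sample size, and a statistical analysis plan that is not shown may set a hierarchy or an adjustment. The error rates above are therefore conditional on an any-one rule, and under an all-three rule they do not arise. This objection stands. It does not remove the contradiction between the sections.

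**The lists differ by one scale.** PDS-5 and PCL-5 are in both. The primary label in Table 2 follows the self-report heading, so it may have been meant to cover self-reports only, and the interview's place is then weak evidence of conflict. That too stands. The PTCI clash is the firm evidence. Pooling both lists into four scales, any of which might win, gives 18.5% if independent, but neither list names four.

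**Independence is implausible.** For scales of the same symptoms the upper end of 8–14% is unlikely, and only about half of any such error favours treatment. The range has to be read with that in mind.

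**Selective effect sizes.** A reader might take "Effect sizes for significant effects will be indicated by" Cohen's d to mean that only the winning scales will be reported. The same section also plans within- and between-group effect sizes without that limit, and this sentence follows the text on moderation and mediation. It does not support a finding.

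**The choice of scale.** Resolving the contradiction requires one named endpoint, not PSS-I-5 in particular. In Table 1 the internet-CBT trials that list an interview (PSSI) show effects of 0.40 and of 0.24 and 0.29, though the latter trial also lists a self-report and both had active comparators. At d = 0.40, 45 per arm would have about 47% power. This is only indicative, but it means that 0.60 should not be carried over to the interview without a check.

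**Conclusion.** The point holds as a contradiction with consequences, not as a demonstrated 14% error rate. The protocol disagrees with itself on whether the PTCI is primary, leaves the interview's status unclear in Table 2, and gives no rule for combining several primaries. Its alpha of 0.05 and power of 80% belong to one unnamed outcome. For three primaries they do not both hold under either of the two simple rules: any-one at 0.05 each gives a two-sided error of about 8–14% (4–7% in favour of treatment, against 2.5% for one test), and all-three gives power of about 54–74%. These figures assume equal correlations from 0 to 0.9, 45 evaluable participants per arm and, for power, d = 0.60 on every scale. It should be settled before outcome data are seen, because it decides what the trial can claim.

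**What to change.** Name one primary endpoint and one time point, in the same words, in the Primary outcomes section and in Table 2, and name that outcome in the Sample size section. PSS-I-5 total severity (0–80) at T3 is the best-supported candidate: its raters are blinded and it is already collected before and after treatment. The sponsor should confirm that d = 0.60 is a reasonable expectation on that scale, or revise the sample size. PDS-5, PCL-5 and PTCI then become secondary in both places.

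If several primaries are kept, state the rule (for example Holm), say whether power refers to one given scale, at least one or all, and restate the sample size accordingly. With a Bonferroni split, 80% power for a given scale needs 60 per arm: 120 evaluable, or 120/0.8 = 150 allowing for 20% attrition.

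With a single primary, and if 0.60 is confirmed, the cost is protocol wording and a table correction, with no new data collection. There are two downsides. A significant PDS-5 or PCL-5 alone could no longer be called primary success. PSS-I-5 is scheduled in Table 2 only before and after treatment, so maintenance of effect would rest on the self-reports unless the interview schedule is clarified; the Procedure section mentions clinician interviews at follow-up without naming the instrument.

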Effect size estimates (Hedges' g) and 95% confidence intervals (CI) for efficacy of CBT relative to placebo on PTSD. *Note* N: number randomized; g : Hedges' g ; FU: follow up in months; ICBT: internet-delivered CBT; TAU: treatment as usual; CBT: cognitive behavioral therapy; ST: supportive therapy; WLC: waitlist control; IE: imaginal exposure; IE+CR: imaginal exposure + cognitive restructuring; SC: supportive counseling; ICT: intensive cognitive therapy; SIT: stress inoculation training; PE: prolonged exposure; CR: cognitive restructuring; CR+PE: cognitive restructuring+ prolonged exposure; Relaxation; PCT: present - centered therapy; NET: narrative exposure therapy; CBSM: cognitive behavioral stress management; SHICBT: self-help ICBT; ICBT exposure: internet- delivered cognitive behavioral therapy with exposure; ICBT non-exposure: internet -delivered cognitive behavioral without exposure; CG: control group, information only; Group PCT: group present-centered therapy; Group CPT: group cognitive processing therapy; TF groups psychotherapy: trauma-focused groups psychotherapy. GCI – General Criterion of Improvement; CAPS- Clinician-Administered PTSD Scale; PCL- PTSD Checklist; IES- Impact of Event Scale; BDI-Beck Depression Inventory; FQ- The Fear Questionnaire; PDS= Posttraumatic Diagnostic Scale; QL- quality of life; QIDS Quick Inventory of Depressive Symptomatology; SRQF- Stressful Responses Questionnaire-Frequency; PSSI PTSD Symptom Scale—Interview Version; MPSS- The Modified PTSD Symptoms Scale

Objectives and research questions

Taking into consideration all the above arguments, the aim of the study is to investigate the clinical efficacy of a guided ICBT program for Romanian adults on measure of PTSD, depression, anxiety symptoms and quality of life.

The program PAXPTSD (Paxonline for Posttraumatic stress disorder) has been adapted according cu DSM-5 criteria for PTSD (APA, 2013) based on empirically validated cognitive behavioral models of PTSD (Clark & Beck, 2011; Leahy, Holland & McGinn, 2011; Resick, Monson, Chard, 2014) and it is currently the only available psychological intervention of this type in Romania (Ciuca, 2019).

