The current study focused on individuals with an established diagnosis of PTSD. The aim of the study is to investigate the effects of guided ICBT on measures of PTSD symptoms, depression, and other anxiety symptoms, as well as quality of life against a control group and the maintenance of the improvements. We expect that the effect size for program PAXPTSD to be in accord with other programs delivered to PTSD patients (Ivarsson et al., 2014; Knaevelsrud et al., 2015; Kuester, Niemeyer & Knaevelsrud, 2016; Spence et al., 2011; Sijbrandij, Kunovski & Cuijpers, 2016).

METHODS/DESIGN

The study is reported in line with the CONSORT 2019 statement (Consolidated Standards of Reporting Trials) and the SPIRIT 2013 Statement (Standard Protocol Items: Recommendations for Interventional Trials).

This study is a two-armed randomized controlled trial (RCT) with one active treatment condition (TC) and a waiting list control group (WL). Individuals from WL will receive the intervention 3 months after the study begins.

1. Guided internet-based cognitive behavioral program for Posttraumatic Stress Disorder (PAXPTSD): Participants will complete the PAXPTSD with guidance from a psychologist. The guidance includes a kickoff meeting discussion of approximately 30 minutes, via Skype, videoconference or telephone after the evaluation, to discuss the results of assessments and to discuss the next steps. After the completion of every module, the psychologists will schedule a session for Q & A with every participant to answer their questions, monitor their progress and offer them feedback. At the end of the program there will be another 30 minutes discussion for debriefing using Skype, videoconference or telephone. All participants will complete the standard program for general symptoms of PTSD and it is composed from 11 modules. Besides these modules, there are 5 facultative modules for specific aspects associated with PTSD (depression, guilt, shame or anger). Facultative modules are activated for every participant by his psychologist according to co-morbidity symptoms.

2. *Waiting list control group*: participants from this group will not receive any kind of intervention for 12 weeks. At the end of the waiting period the participants will receive the intervention program if they want this (after 3 months of study begins) and we will check if they receive any treatment for PTSD and associated problems in this period.

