Clinician interviewing and self-report assessments will take place at screening (T0), pre-treatment assessment (T1), post-assessment 11 weeks after randomization (T3) and 3 months follow-up (T4). There will be also weekly mood assessment. All self-report measures are administered through internet (secure links are used and all the data are

encrypted) and the diagnostic interviews are conducted face to face or via telephone. The questionnaires, which were not yet validated for Romanian population, were previously translated in Romanian and underwent a rigorous back-translation process to ensure a good adaptation. The version we acquired was approved by the author(s) of questionnaires. See **Table 2** for an overview of all assessments. Adherence to assessment completion will be monitored throughout the study. In case of noncompliance participants will be contacted after 7 days (14, 21) to remind them of assessment completion. After 28 days a short message will be sent via text message. The entire communication between psychologist and participants will be inside the platform. In maximum 48 hours after completing the module the psychologist and the participants will schedule the Q and A session for any questions, they will also give feedback and monitor the progress.

Persons who are interested in the program can freely access the study website. The website offers information about PTSD and treatment options and a description of the present clinical trial and information about enrollment.

Participants must offer an online informed consent, and then provide demographic information (age, gender, location and contact information). Then, they have to complete key questionnaires: (1) a screening for the exclusion criteria; (2) one scale to evaluate Posttraumatic Stress Disorder and its severity (PDS-5); and (3) a screening questionnaire for psychiatric comorbidities using Psychiatric Diagnostic Screening Questionnaire (PDSQ).

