The Patient Health Questionnaire (PHQ-9) is a widely used measure to evaluate and monitor depression (Kronke, Spitzer, Williams, Lowe, 2010). The questionnaire contains nine items and the participants are required to rate the frequency of present difficulties in the past 2 weeks. Scores on this questionnaire indicate the presence and the severity of the symptoms with a range of scores between 0 and 27. Cutoff points for mild, moderate, moderately severe and severe depression are 5, 10, 15 and 20. The internal reliability of the English version of PHQ-9 in a

clinical population was in a range between 0.86-0.89. (Ciuca, Berger, Crisan & Miclea, 2016; Ciuca et al., 2011), which indicates good reliability. The test-retest reliability was also good, 0.84, and the correlation with interview results is very high, 0.84. We will use PHQ-9 for screening and monitoring the symptoms once a week.

Anxiety is also measured in a self-report manner using generalized anxiety disorder measurement GAD-7 (Spitzer, Kroenke, Williams, & Löwe, 2006) with items ranging from 0 to 3 (Frans, Rimmo, Aberg & Fredrikson, 2005; Weisel et al., 2018). Internal consistency of GAD-7 was excellent (Cronbach α =.92). Test-retest reliability was good 0.83 (Frans, Rimmo, Aberg & Fredrikson, 2005).

Functional impairment

Work and Social Adjustment Scale (WSAS) was developed by Mundt, Marks, Shear and Greist (Mundt, Marks, Shear & Greist, 2002). The scale has 5 items, which are simple and reliable. We decided to use this scale to evaluate the functional impairment caused by PTSD symptoms. The scale items' encompass different domains of functioning and include the following: ability to work, home management, social leisure and ability to form and maintain close relationships. Each item is rated on a 9-point Likert scale and the scores range between 0 (no impairment) and 8 (very severe impairment). The sums of the 5 items represent total impairment with higher scores representing greater impairment. The maximum score is 40. The WSAS has demonstrated good internal consistency (range between 0.70 and 0.94) and test-retest reliability (0.73) and is a scale which is sensitive to patients' perceptions of disorder severity (Ciuca et al., 2011 ;Mundt, Marks, Shear & Greist, 2002).

Cognitions relevant to Posttraumatic Stress Disorder

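### Quality of life is in the study aim and the secondary outcomes, but no scheduled instrument measures it

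*Protocol*

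**What the plan says.** Objectives and research questions states the aim twice. The first statement is to investigate efficacy "on measure of PTSD, depression, anxiety symptoms and quality of life". The second repeats the symptom domains and adds "as well as quality of life against a control group and the maintenance of the improvements", so quality of life is meant to be compared between groups and followed over time.

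Secondary outcomes then begins its list with "Secondary outcome measures include depressive symptoms, functional impairment, quality of life" and continues with trauma-related cognitions, stress and other anxiety. Functional impairment and quality of life are two separate entries in that list.

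On data collection, the Procedure section sends the reader to Table 2 "for an overview of all assessments". Table 2 gives the WSAS the purpose "Functional impairment". The section describing that scale agrees: "We decided to use this scale to evaluate the functional impairment caused by PTSD symptoms".

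**The concern.** A stated between-group objective needs a measurement behind it. If the assessment schedule is followed exactly, the database will hold no quality-of-life score at any visit. That part of the aim will then go unreported, or the report will have to treat some other scale as quality of life without the protocol having said so.

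This is not detail that can be left to a statistical analysis plan. Such a plan decides how collected data are analysed; it cannot create data from a questionnaire that participants never receive.

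**Working it through.** The check sets the promised outcomes against the scheduled instruments. It uses no alpha, power or effect size, and the protocol gives no figure to reproduce.

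**Step 1: map each construct in the Secondary outcomes sentence to an instrument.**

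| Construct listed | Instrument in Table 2 and the text |
|---|---|
| Depressive symptoms | PHQ-9 |
| Functional impairment | WSAS |
| Quality of life | none |
| Trauma-related cognitions | PTCI |
| Stress level | PSS-10 |
| Other anxiety symptoms | GAD-7 |

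Result: 6 constructs, 5 with an instrument, 6 − 5 = 1 without.

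**Step 2: go through Table 2 from the other side.** It names 14 distinct instruments: PSS-I-5, AUDIT, PDSQ (which appears twice, as interview and as self-report), PDS-5, PTCI, PCL-5, PHQ-9, GAD-7, WSAS, PSS-10, CEQ, SS-5, PFQ and PANEPS. AUDIT serves only screening and exclusion, which leaves 14 − 1 = 13 outcome or additional measures. None of the 13 has quality of life in its purpose column.

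**Step 3: read the instrument descriptions.** They cover diagnosis and comorbidity, PTSD severity, mood and anxiety, functional impairment, trauma cognitions, perceived stress, credibility and expectancy, social support, sociodemographics, adherence, satisfaction, drop-out reasons and side effects. None describes a quality-of-life scale.

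**Step 4: test the possible stand-ins.**
- WSAS: assigned to functional impairment in both Table 2 and the text, and functional impairment is already its own entry in the list.
- SS-5: perceived social support, described as a possible predictor or moderator and placed under additional measures.
- PSS-10: perceived stress, which is also its own entry in the list.

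The only other mention of a quality-of-life measure is an abbreviation in the legend to Table 1. It belongs to an outcome of a cited CBT trial, not to this one.

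**Step 5: consider whether the instrument was lost in reproducing the document.** Table 2 and the running text both lack it. The missing Figure 1 is captioned as the study flow, and the protocol directs the reader to Table 2 for the assessments. Loss is an unlikely explanation.

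**Step 6: relate the gap to the aim.** The first statement of the aim names four domains: PTSD, depression, anxiety and quality of life. Three have instruments and one does not. Functional impairment, which does have an instrument, is not named in either statement of the aim.

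**The case against.** The strongest reply is that quality of life in the aim is loose wording for what the WSAS measures. The aim never mentions functional impairment although the WSAS is a planned secondary measure, and that scale covers work, home management, social leisure and close relationships. On this reading the defect is one inconsistent list rather than an objective without data. The reading is possible, and the WSAS may be what the authors had in mind. But the protocol nowhere says so, and the Secondary outcomes sentence counts against it by listing the two constructs separately. If the WSAS was intended, the aim needs the same rewording anyway.

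Three stronger readings are tempting, and the document does not support them:
- *Three separate commitments.* A reader might count an aim, an objective and an outcome. The two passages in Objectives and research questions state one aim twice, so there is one aim and one list entry.
- *A planned or likely outcome switch.* A reader might infer that some scale will be relabelled once results are known. Nothing in the protocol suggests this. The WSAS has a stated purpose, scoring and time points, which limits the room for it.
- *Damage to the main result.* Quality of life is not a primary outcome, does not enter the Sample size section, and is not among the expected results for this program in the Discussion.

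**Conclusion.** The point holds as an internal inconsistency with a real but limited consequence. One of the four domains in the first statement of the aim, and one of the six secondary constructs, has no instrument. The trial as scheduled therefore cannot support any statement about quality of life, either against the waiting list or at follow-up. The primary PTSD comparison and the other five secondary constructs are untouched.

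The conclusion rests on taking Table 2 as complete, as the Procedure section presents it, and on reading the Secondary outcomes sentence as written. It is worth correcting, but it ranks below any problem that affects the primary comparison.

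**What to change.** **Preferred: remove the claim.**
- In Secondary outcomes, delete quality of life. Functional impairment is already in the list, so substituting it there would only duplicate an entry.
- In both statements of the aim, replace quality of life by functional impairment (WSAS), at the time points Table 2 already schedules: pre-treatment, mid-intervention, post-treatment and 3-month follow-up. Limiting the wording to post-treatment would drop the maintenance part of the aim.
- Make no quality-of-life claim in the report.

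This is wording in three places and needs no new data. The trial gives up a claim for which it would have had no data.

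**Alternative: keep the objective.** Before enrolment, add to Table 2 one short validated quality-of-life self-report, completed on the existing platform at T1, T3 and T4, with a matching description in the text. T3 serves the comparison with the waiting list, and T4 is needed because the aim includes maintenance. The cost is a small added burden for participants. This option assumes enrolment has not begun; the Ethical approval section describes approval as still to be obtained, which is consistent with that.
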